11.3. Efficacy Analyses

Primary Endpoint

For Part 2, the primary endpoint in this study is RSV RNA log₁₀ viral load (measured by qRT-PCR in the mid-turbinate nasal swab specimens) AUC immediately prior to first dose of study drug (baseline) over 7 days. Mean log₁₀ viral load values over time will be analyzed using a restricted maximum likelihood based repeated measures approach. Analyses will include the fixed, categorical effects of treatment, strata, visit, and treatment-by-visit interaction, as well as the continuous, fixed covariates of baseline log₁₀ viral load and baseline log₁₀ viral load by-visit interaction. An unstructured (co)variance structure will be used to model the within-subject errors over time. The differences in the AUCs for active versus placebo will be derived using

appropriate contrasts deriving least square mean differences, including the 95% 2-sided confidence intervals. For inferential purposes, p-values will be compared with significance levels controlling for the (family-wise) type 1 error rate. Details will be provided in the SAP that will be finalized before the first formal interim analysis of Part 2.

Secondary Endpoints

The secondary endpoint of time to clinical stability is defined as the time at which the following criteria are all met:

- normalization of blood oxygen level (return to baseline, pulse oximetry) without requirement of supplemental oxygen beyond baseline level
- normalization of oral feeding
- normalization of respiratory rate
- normalization of heart rate

Normalization criteria will be specified in the SAP. Subjects for which no time point could be established (eg, withdrawal of informed consent before reaching the endpoint or no clinical stability at last observation) will be (right-) censored at the latest time point at which it could be established that clinical stability was not reached. The differences in time to clinical stability of active dose regimens versus placebo treatment will be estimated using a Cox proportional hazard model; as baseline covariates, stratification factors, absence/presence of other viral or bacterial infections, baseline \log_{10} viral load, and time from onset of first symptoms to treatment will be added. Treatment effect versus placebo will be reported, including 95% confidence intervals. In case the proportional hazards assumption is not satisfied, appropriate sensitivity analyses will be performed as detailed in the SAP.

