A secondary endpoint of high interest is the length of hospital stay. The length of hospital stay is in hours and taken from the start of treatment initiation to discharge and to readiness for discharge. The differences of active dose regimens versus placebo treatment will be estimated using the accelerated failure time model using appropriate contrasts; baseline covariates such as stratification factors, absence/presence of other viral or bacterial pathogens, RSV baseline log₁₀ viral load, and time from onset of first symptoms to treatment will be added when of predictive value based on blinded data. Treatment effects versus placebo will be reported as acceleration factors including 95% confidence intervals. Subjects for which no time point could be established (eg, withdrawal of informed consent before reaching the endpoint) will be (right-)censored at the latest time point at which it could be established that the endpoint was not reached. Subjects for whom discharge cannot be considered as a marker of adequate recovery (eg, subjects who die during hospitalization or who are transferred to a care facility with the same level of care as during hospitalization) will be censored at the planned final follow-up visit. No adjustments for multiplicity will be made. Analytical details will be provided in the SAP.

While this clinical endpoint is considered of high interest, the current sample size is determined by considerations on antiviral activity; for length of hospital stay the anticipation is that there will be too much heterogeneity to expect statistically significant separation of active groups versus placebo with the current sample size, even if a numerical trend is anticipated.

The impact of the baseline viral genotype and subtype on the antiviral activity will be explored.

Analysis of the viral sequencing results will be described in the SAP.

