1. INTRODUCTION

This statistical analysis plan (SAP) contains definitions of analysis sets, derived variables and statistical methods for the analysis of efficacy and safety of the investigational compound ALS-008176 (also known as JNJ-64041575). The SAP is to be interpreted in conjunction with the protocol. A detailed analysis plan for the Interim Analysis will be described in the Interim Analysis Plan (IAP). A detailed analysis plan for the pharmacokinetic and pharmacokinetic/pharmacodynamics data will be described in a Clinical Pharmacology Analysis Plan (CPAP).

ALS-008176 is a 3',5'-bisisobutyrate prodrug, which is readily metabolized to the cytidine nucleoside analog, ALS-008112. Subsequently, inside cells, ALS-008112 is efficiently converted to its nucleoside triphosphate, ALS-008136. This nucleoside triphosphate is a potent inhibitor of respiratory syncytial virus (RSV) ribonucleic acid (RNA)-dependent RNA polymerase activity and works via a classic chain termination mechanism. ALS-008144, the uridine metabolite of ALS-008112, is the inactive major metabolite noted in systemic circulation.

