4.2.4. Secondary Efficacy Endpoints

4.2.4.1. Definition

Formulae to be used for derived variables, including data conversions, are provided in [Table 1](#). In the derivation of durations described below, no imputation of the start and/or end date/time will be performed.

Table 1. Calculations and Conversion Formulae

Measurement	Formula
Length of hospital stay (hours) [Time-to event]	(Date and time of event or censoring - date and time of first dose of study drug)/3600, rounded to one decimal
Time to readiness for discharge (hours) [Time-to-event]	Subjects who complete or withdraw from the study prior to the event will be censored at the date of completion or withdrawal. If the time is not available they will be censored at 12:00. In case of death prior to an event the time of death will be taken as censoring time (or 12:00 if not available).
Length of hospital stay since hospital admission (hours) [Time-to event]	(Date and time of event or censoring - date and time of hospital admission)/3600, rounded to one decimal
Time to readiness for discharge since hospital admission (hours) [Time-to-event]	Subjects who complete or withdraw from the study prior to the event will be censored at the date of completion or withdrawal. If the time is not available they will be censored at 12:00. In case of death prior to an event the time of death will be taken as censoring time (or 12:00 if not available).
ICU duration of stay (hours) [Duration]	sum of [(end date and time of event - start date and time of event)/3600], rounded to one decimal
Duration of supplemental oxygen (hours) [Duration] (3 separate parameters: supplemental oxygen, invasive ventilator, non-invasive ventilator)	If the end date is missing, the end date is considered to be after study completion or withdrawal. If the initial start time is prior to the first dose of study drug, the duration prior to the first dose of study drug will be deducted from the overall duration.
Need for feeding, hydration by IV catheter/enteral tube (hours) [Duration] (2 separate parameters)	If the end date and time is after the study completion/discontinuation, the duration after the date and time of study completion/discontinuation will be deducted from the overall duration. If the time is not available it will be put at 12:00.
Time to end of Oxygen supplementation (hours)	(Date and time of event or censoring - date and time of first dose of

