
Time to return to pre-RSV disease level (hours) for HR, RR, SpO2 [Time-to-event]
	
(minimum[date and time of time point of return to pre-RSV disease level, date and time of last measurement] - date and time of first dose of study drug)/3600, rounded to one decimal
 
If none of the values are indicated to be abnormal for the subject, this value will be set at time 0.
 
Subjects with an abnormal value at the last assessment will be censored. Subjects for which this last assessment is the baseline

	assessment will be censored at time 0.
Time to return to pre-RSV disease feeding status (hours) [Time-to-event]	
(Date and time of event or censoring - date and time of first dose of study drug)/3600, rounded to one decimal
 
All subjects are assumed to have no supplemental feeding pre-RSV.
 
The event is defined as the last available end date and time supplemental feeding was provided. If this date is missing, the end date is considered to be after study completion or withdrawal
 
Subjects who complete or withdraw from the study prior to the event will be censored at the date of completion or withdrawal. If the time is not available they will be censored at 12:00. In case of death prior to an event the time of death will be taken as censoring time (or 12:00 if not available).
 
If no supplemental feeding was necessary post baseline, the value will be set to 0.

Time to Clinical Stability [Time-to-event]	
maximum[time to return to pre-RSV disease level for SpO₂, RR and HR, feeding]
 
Subject will be censored if the subject is censored for at least 1 of the 4 time to parameters at the minimum of the available data. If no data are available the time will be censored at 0 hours.

Time point of return to normal temperature (hours) [Time-to-event]	
All subjects are assumed to have a normal temperature level pre-RSV disease
 
Time point of return to pre-RSV disease level temperature is defined as the first time point with a normal temperature and no time points after that time point with an abnormal value.
 
The normal limits to be used are:
 
 - Axillary: 36.1 – 38.0 - Forhead: 36.1 – 38.0

	
 - Oral: 36.1 – 38.0 - Rectal: ≤ 37.2 - Tympanic: ≤ 37.8 
If there were no abnormal values post baseline, the value will be set at 0 hours.

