If specified, time-to-events variables will also be compared between each active treatment group and placebo using an accelerated failure time (AFT) model. The distribution to be used will be determined based on the goodness of fit using Akaike's information criterion and will be selected from the following parametric families: lognormal, log-logistic, or Weibull. The AFT model will include the fixed, categorical effects for treatment (with placebo as the reference) and strata, as well as the continuous covariates of baseline \log_{10} viral load. Other covariates may be included when of predictive value, such as smoker (yes/no), presence/absence of co-morbid diseases, presence/absence of co-morbid diseases associated with risk for lower respiratory tract disease, presence/absence of other conditions/therapy of potential interest, days since symptom initiation, RSV subtype, use of corticosteroids, supplemental oxygen at baseline and age as continuous variable. As in the logistic regression, a significance level of 0.05 will be used for a variable to enter the model and a significance value of 0.10 to stay in the model. A summary of information from the final model will include parameter estimates and associated standard errors, estimated accelerated failure time ratios versus placebo and associated 95% confidence intervals, and p-values.

Length of Hospital Stay/Length of Hospital Need

The Length of Hospital Stay/Need (both since treatment initiation and since hospital admission) will be summarized and listed. The Length of Hospital Stay/Need will be analyzed in an exploratory manner using Kaplan-Meier analysis.

Length of Hospital Stay/Need will also be compared between each active treatment group and placebo using an accelerated failure time (AFT) model as described above.

Need and Duration of ICU Stay

The need for ICU stay will be analyzed on the subgroup of subjects who were not in the ICU before the first dose of study medication. The duration in the ICU will be analyzed all subjects and on both the subgroup who were and who were not in the ICU before the first dose of study medication.

The number and percentage of subject with need of ICU stay, and the duration of ICU stay in hours, will be summarized descriptively.

To compare incidence of the need for ICU stay across treatment groups, (exact) logistic regression as described before will be used.

Need and Duration of Oxygen Support, Supplemental Feeding, Supplemental Hydration

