4.2.5.2. Adult RSV Additional Questions

4.2.5.2.1. Definition

Table 4. Calculations and Conversion Formulae

Measurement	Formula
Time to return to usual activity	
The time in hours from the first dose of investigational product till the first one of 2 successive cases where the response is ‘Yes’ on RSV-PRO additional question 7 (“have you returned to your usual activities?”) . Time points with missing data are ignored in this analysis. The successive recordings cannot be within the same window. In case there are 2 recordings within a single window (i.e. morning window, afternoon window or evening window) the worst case within that window will be taken.
 
In cases where there are no sufficient recordings, the endpoint will be censored. Censoring will be at time of the last assessment if ticked as “Yes”; otherwise censoring will be the first window after the last assessment (lower limit). One exception is censoring at the Day 28 Visit (last study day for the subject). If the subject is not returned to usual activities/health on this day, the time of the last diary entry will be taken as the time of censoring.

Time to return to usual health	
The time in hours from the first dose of investigational product till the first one of 2 successive cases where the response is ‘Yes’ on RSV-PRO additional question 9 (“have you returned to your usual health?”). Time points with missing data are ignored in this analysis. The successive recordings cannot be within the same window. In case there are 2 recordings within a single window (i.e. morning window, afternoon window or evening window) the worst case within that window will be taken.
 
In cases where there are no sufficient recordings, the endpoint will be censored. Censoring will be at time of the last assessment if

	both items are ticked as “Yes”; otherwise censoring will be the first window after the last assessment (lower limit). One exception is censoring at the Day 28 Visit (last study day for the subject). If the subject is not returned to usual activities/health on this day, the time of the last diary entry will be taken as the time of censoring.
Time to full recovery	The maximum of the time to return to usual activity and usual health when both have an event, or the minimum of censored time(s) if at least one is censored.

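### SAP Table 1 and protocol 11.3 give conflicting censoring rules for time to clinical stability, and for deaths in length of stay and readiness for discharge

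*SAP*

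**What the plan says.** **Time to clinical stability.** SAP Table 1 (section 4.2.4.1) takes the largest of four component times: SpO2, respiratory rate, heart rate and feeding. On censoring, the participant "will be censored if the subject is censored for at least 1 of the 4 time to parameters at the minimum of the available data". Some components can legitimately equal zero. For feeding, "If no supplemental feeding was necessary post baseline, the value will be set to 0", and a vital sign never flagged as abnormal also gets time 0. Protocol 11.3 says a subject with no established time of stability is to be "censored at the latest time point at which it could be established that clinical stability was not reached".

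**Length of hospital stay and readiness for discharge.** SAP Table 1 states: "In case of death prior to an event the time of death will be taken as censoring time". Protocol 11.3 says that subjects whose discharge does not mark recovery, namely those who die in hospital or move to a facility "with the same level of care as during hospitalization) will be censored at the planned final follow-up visit". Table 1 has no rule for such transfers. SAP section 1 states "The SAP is to be interpreted in conjunction with the protocol", so transfers are an omission and not a contrary rule.

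**The concern.** Subjects known not to have recovered should stay in the risk set for as long as the non-recovery was observed. In the length-of-stay analysis the protocol goes further and keeps in-hospital deaths there to the end of follow-up. Under the SAP's death rule, and under the literal reading of its clinical stability rule, these subjects leave early. Each arm's Kaplan-Meier recovery estimate can then only rise.

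The between-arm comparison is an accelerated failure time (AFT) model, with the distribution "selected from the following parametric families: lognormal, log-logistic, or Weibull". In all three families S(0) = 1, so a subject censored at hour 0 contributes a factor of 1 to the likelihood. That non-recovery then adds nothing to the comparison.

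The protocol singles out length of stay as a secondary endpoint of particular interest. The protocol leaves normalization criteria and analytical details to the SAP, but it sets these censoring rules itself. The SAP neither flags nor justifies a departure.

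**Working it through.** No sample size, power or alpha figure depends on these rules, so there is no plan figure to reproduce. The check compares the rules and then sizes the difference.

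**1. Two readings of the clinical stability rule.** The literal reading takes the smallest of all four component values. The narrow reading takes the smallest of the censored components only. The SAP writes the narrow rule explicitly for another composite, time to full recovery (section 4.2.5.2.1): "the minimum of censored time(s) if at least one is censored". The corresponding clause for clinical stability has no such restriction.

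**2. Constructed subjects** (hours; c = censored):

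| SpO2 | RR | HR | Feeding | SAP literal | SAP narrow | Protocol |
|---|---|---|---|---|---|---|
| 48 | 312c | 0 | 0 | 0 | 312 | 312 |
| 48 | 312c | 72 | 36 | 36 | 312 | 312 |
| 312c | 144c | 60 | 24 | 24 | 144 | 312 |

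The literal reading fails in all three cases. The narrow reading fails when two components are censored at different times.

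**3. Size under the literal reading.** Let f be the share never stable by Day 28 and p0 the share of those censored at hour 0. Keep the other never-stable subjects at risk to Day 28, which is conservative. The protocol rule gives 1 − f. The literal rule removes f·p0 from the risk set at the start, giving (1 − f)/(1 − f·p0). For f = 10% and p0 = 50%, this is 0.90/0.95 = 94.7%. Values of f and p0 are assumed.

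| | Protocol | p0 = 25% | 50% | 75% | 100% |
|---|---|---|---|---|---|
| f = 10% | 90% | 92.3% | 94.7% | 97.3% | 100% |
| f = 20% | 80% | 84.2% | 88.9% | 94.1% | 100% |
| Difference, points | 10 | 8.1 | 5.8 | 3.2 | 0 |

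The last row takes f = 10% on active and 20% on placebo. With equal f and p0 in both arms, both estimates rise together and the difference is unchanged.

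**4. Size under the narrow reading.** A four-component simulation used 200,000 subjects. It assumed no supplemental feeding in 50 to 95%, a vital sign never abnormal in 0 or 25%, and 0 or 50% of never-stable subjects lost before Day 28. The largest gap from the protocol rule was 0.001 (0.1 point).

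**5. Length of stay.** Assumed: 30 per arm, lognormal stay with median 120 h and log-SD 0.7, below 600 h, the same in both arms; deaths uniform on 48 to 336 h, censored at death (SAP) or at 28 × 24 = 672 h (protocol); AFT family chosen by AIC; 400 replicates. With 1 to 4 deaths in an arm, estimated discharge by Day 28 is 0.99 to 1.00 under the SAP. Under the protocol it is 29/30 = 0.97 down to 26/30 = 0.87. AFT time ratios, active over placebo:

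| Deaths, placebo / active | SAP | Protocol |
|---|---|---|
| 1 / 1 | 0.990 | 0.988 |
| 3 / 3 | 0.998 | 0.999 |
| 2 / 1 | 0.958 | 0.939 |
| 3 / 1 | 0.941 | 0.902 |
| 4 / 1 | 0.915 | 0.856 |

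A second lognormal simulation used medians of 96 and 168 h, log-SD 0.8, and Day 28 taken as 27 × 24 = 648 h. Mortality was 13.8% on placebo (the highest 60-day figure in protocol 1.2) against an assumed 3% on active. It gave 0.89 (SAP) versus 0.77 (protocol) at 96 h, and 0.93 versus 0.83 at 168 h. With equal mortality (0% or 5%) the rules agreed within 0.01.

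**The case against.** **The clinical stability sentence is ambiguous.** Every sizeable figure for that endpoint needs the literal reading. The next sentence of Table 1 assigns hour 0 to subjects without data, which suggests the authors did not mean assigned zeros to drive the minimum. The full-recovery rule could likewise show what they intended. This stands as an argument about intent. It does not remove the conflict, because even the smallest censored time is not the latest, and a programmer could implement either reading.

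**The SAP predates the current protocol.** It still has a minimum age of 50 and a first interim triggered by 45 subjects randomized, so it may have matched the protocol it was written against. That may explain the mismatch, but the current texts still need reconciling.

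**The death rule is a choice of estimand.** The simulations in step 5 assume no effect among survivors, and there the SAP ratio is nearer 1.00. The protocol deliberately lets deaths influence the ratio. This is fair: the defect is two documents prescribing different estimands, not proven bias.

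**The effect is small against the noise.** With 3 versus 1 deaths, a lognormal rerun put the standard error of the log time ratio at about 0.17. The gap between rules is ln(0.941/0.902) = 0.04 in the table above and ln(0.93/0.85) = 0.09 in that rerun, so about a quarter to a half of one standard error. The protocol itself does not expect significance on length of stay. This limits the severity but does not settle which rule applies.

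**Conclusion.** The concern holds. The death rules for length of stay and readiness for discharge conflict outright. The clinical stability rules differ under either reading of the SAP: seriously under the literal one, negligibly (within 0.1 point) under the narrow one.

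Following the SAP's death rule, or its clinical stability rule read literally, would raise each arm's recovery estimate. Treatment contrasts change only when deaths or non-recoveries are unbalanced between arms. The sizes rest on assumed non-recovery shares, death counts and stay distributions, and they illustrate direction and order of magnitude only.

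The primary viral load AUC analysis, alpha and sample size are unaffected. Deaths are still reported as all-cause mortality and on the ordinal scale. This should be fixed, but it does not threaten the trial's main conclusion.

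**What to change.** Amend SAP Table 1 before unblinding:

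- **Clinical stability:** censor at the latest assessment at which at least one of the four criteria was unmet. Use time 0 only when there are no post-baseline data.
- **Length of stay and readiness for discharge from treatment initiation:** censor in-hospital deaths and transfers at the same level of care at the planned Day 28 visit, as in protocol 11.3. Keep the SAP's condition that death precedes the event, so that a subject already declared ready who then dies keeps the readiness event.
- **Since-admission versions:** state which rule applies.

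Times for oxygen, feeding and hydration are outside this correction. If the sponsor prefers the SAP's rules, it should say so and justify them before unblinding. Protocol 11.3 also names a Cox model for clinical stability where the SAP uses AFT; that can be settled in the same revision.

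The cost is SAP wording and derivation programming, with no new data. Reported recovery proportions would be lower than under the present SAP text, by up to the amounts shown.

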Pruritus	slight itching at injection site	moderate itching at injection extremity	itching over entire body	

SYSTEMIC				
	Grade 1	Grade 2	Grade 3	Grade 4
Allergic Reaction	pruritus without rash	localized urticaria	generalized urticaria; angioedema	anaphylaxis
Headache	mild, no treatment required	transient, moderate; treatment required	severe; responds to initial narcotic therapy	intractable; requires repeated narcotic therapy
Fever: oral	37.7 - 38.5 C or 100.0 - 101.5 F	38.6 - 39.5 C or 101.6 - 102.9 F	39.6 - 40.5 C or 103 - 105 F	> 40 C or > 105 F
Fatigue	normal activity reduced < 48 hours	normal activity decreased 25- 50% > 48 hours	normal activity decreased > 50% can't work	unable to care for self

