Time to normal temperature (hours) [Time-to event]	
Minimum[date and time of Time of return to pre-RSV disease level temperature, date and time of last measurement] - date and time of first dose of study drug)/3600[†], rounded to one decimal
 
If none of the values are abnormal for the subject, this value will be set at time 0.
 
Subjects with an abnormal value at the last assessment will be censored. Subjects for which this last assessment is the baseline assessment will be censored at time 0.

Time point of return to pre-RSV functional status (KATZ ADL score)	
The first time point where the KATZ ADL score is equal or higher than the pre-RSV disease KATZ ADL score and no lower scores are measured after this time point.
 
Functional status is the total points on the KATZ Index of Independence in Activities of Daily Living (KATZ ADL score)

Time to return to pre-RSV functional status (KATZ ADL score) (days) [Time-to-event]	
minimum[date and time of time of return to pre-RSV functional status, date and time of last measurement] - date and time of first dose of study drug)/3600, rounded to one decimal
 
If the KATZ ADL score is never lower than the pre-RSV score, this value will be set at time 0.
 
Subjects with a functional status lower than the pre-RSV disease functional status at the last KATZ ADL assessment will be censored. Subjects for which this last assessment is the baseline assessment will be censored at time 0.

Ordinal scale score	
The value as collected in the eCRF on the day of last dose (Day 5/6 depending on timing of LD) will be used as score on the day of last dose. Only in case of a missing score, the score will be calculated based on the available information in the eCRF.
 
The 6 categories to be considered are:

	
 • Death • Admitted to ICU • Non-ICU hospitalization requiring supplemental oxygen • Non-ICU hospitalization not requiring supplemental oxygen • Not hospitalized, unable to resume normal activities • Not hospitalized, resumption of normal activities 
Subjects will receive a score ranging from 1 (=subject died on or before of their day of last dosing) to 6 (=subject was not-hospitalized, resumption of normal activity) depending on his status on day of last dosing
 
For days 3 to 14, the ordinal scale will be calculated on each day, using the algorithm described above.

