4.3.3. Vital Signs

Systolic and Diastolic blood pressure, pulse rate, respiratory rate, tympanic temperature and oxygen saturation will be investigated.

Definitions

The following abnormalities will be defined:

Abnormality Code	Vital Signs parameter		
	Pulse	DBP	SBP
Abnormalities on actual values			
Abnormally low	< 45 bpm	≤ 50 mmHg	≤ 90 mmHg
Grade 1 or mild	-	> 90 mmHg - < 100 mmHg	> 140 mmHg - < 160 mmHg
Grade 2 or moderate	-	≥ 100 mmHg - < 110 mmHg	≥ 160 mmHg - < 180 mmHg
Grade 3 or severe	-	≥ 110 mmHg	≥ 180 mmHg
Abnormally high	≥ 120 bpm	-	-

Abnormality Code	Respiratory
Abnormalities on actual values	
Normal	< 17 breaths per minute

Abnormality Code	Respiratory
Grade 1 or mild	17-20 breaths per minute
Grade 2 or moderate	21-25 breaths per minute
Grade 3 or severe	> 25 breaths per minute
Grade 4 or potentially life threatening	intubation-

Abnormality Code	Tympanic Temperature (°C)
Abnormalities on actual values	
Normal	< 37.5
Abnormally high	≥ 37.5

Abnormality Code	Oxygen Saturation (%)
Abnormalities on actual values	
Abnormally low	< 95
Normal	≥ 95

In determining the abnormalities, the following rules are applied:

- worst grades/abnormalities are determined over the whole observational period for each trial phase separately, including post-baseline scheduled and unscheduled measurements of that phase.
- The abnormalities ‘abnormally low’ and ‘abnormally high’ /grades are considered equally important, i.e. if a subject has as well an abnormally low as an abnormally high or graded value post-baseline, both abnormalities are shown in the tables. (This means that the sum of the percentages can be more than 100%)

An abnormality will be considered treatment-emergent in a particular phase if it is worse than baseline. If baseline is missing, the abnormality is always considered as treatment-emergent. A shift from ‘abnormally low’ at baseline to ‘abnormally high’ or ‘grade ...’ post baseline (or vice versa) is also treatment-emergent.

Analysis Methods

Actual values and change from baseline will be summarized by treatment group at each scheduled time point. The number and percentage of will be shown in a cross-tabulation of the toxicity/abnormality post-baseline versus baseline at each scheduled time point.

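### SAP Table 1's normal-temperature limits disagree with SAP 4.3.3 for tympanic readings, and the 36.1 floor on three routes lets one low reading undo a resolved fever

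*SAP*

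**What the plan says.** Return of body temperature to its pre-RSV level is a secondary endpoint (protocol 2.1.2, SAP 4.2). SAP 4.2.4.1, Table 1 assumes that every subject had a normal temperature before RSV and dates recovery at the "first time point with a normal temperature and no time points after that time point with an abnormal value". What counts as normal depends on the measuring route: "Oral: 36.1 – 38.0", "Axillary: 36.1 – 38.0", the same range for forehead readings, at most 37.2 for rectal readings, and "Tympanic: ≤ 37.8". So three routes have a floor and a ceiling, and two have a ceiling only.

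Two more rules complete the variable. For subjects who are never abnormal: "If there were no abnormal values post baseline, the value will be set at 0 hours". At the other end: "Subjects with an abnormal value at the last assessment will be censored". Neither rule separates a high value from a low one.

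For safety, SAP 4.3.3 states that "pulse rate, respiratory rate, tympanic temperature and oxygen saturation will be investigated". There a tympanic reading is normal below 37.5 °C and abnormally high from 37.5 °C. That section defines low categories for pulse, blood pressure and oxygen saturation, but none for temperature.

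Protocol Attachment 1 grades an oral temperature of "37.7 - 38.5 C or 100.0 - 101.5 F" as Grade 1 fever. Protocol 9.2 fixes no route and asks only that the method be noted. Footnote q of the Time and Events Schedule has vital signs taken twice daily in hospital, then once each on Days 7, 10, 14 and 28 after discharge.

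**The concern.** A time-to-recovery variable that any later abnormal value can cancel is only as good as its definition of abnormal. Here that definition differs between two sections of one SAP for the same route, and for three of five routes it includes low readings that have nothing to do with fever. Because the route is left open, a reading of 36.0 is abnormal if taken orally and normal if taken tympanically, possibly in the same subject on different days.

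At stake are the event times and the censoring indicators that feed the Kaplan-Meier and accelerated failure time analyses of this endpoint (SAP 4.2.4.2). Spurious delays and censoring add variation that does not reflect resolution of illness. The efficacy and safety tables of one report could also describe the same tympanic reading in opposite terms.

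**Working it through.** The plan states no figure for this endpoint that could be reproduced, so the check compares the limits and then applies the rule to worked cases. Readings are taken to be recorded to 0.1 °C.

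**1. Limits side by side**

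| Route | SAP Table 1, normal | Other limit in the documents | Overlap |
|---|---|---|---|
| Tympanic | ≤ 37.8 | SAP 4.3.3: abnormally high from 37.5 | 37.5, 37.6, 37.7, 37.8 |
| Oral | 36.1 to 38.0 | Attachment 1: Grade 1 fever 37.7 to 38.5 | 37.7, 37.8, 37.9, 38.0 |
| Axillary, forehead | 36.1 to 38.0 | none | – |
| Rectal | ≤ 37.2 | none | – |

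The rectal ceiling lies 38.0 − 37.2 = 0.8 °C below the oral, axillary and forehead ceiling, without explanation.

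**2. Direction of each effect**

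- *Tympanic.* Every value above 37.8 is also at or above 37.5. The last abnormal reading under Table 1 can therefore never come after the last one under the 4.3.3 limit. Recovery under Table 1 is at the same time or earlier.
- *Floor.* Adding a lower bound only adds abnormal values. Recovery with the floor is at the same time or later, or is lost to censoring.

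**3. Rule applied to assumed series**

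Assumed post-baseline readings are every 12 h to 120 h, then at 144, 216, 312 and 648 h (Days 7, 10, 14 and 28). The rule gives 0 h if no value is abnormal, otherwise the first reading after the last abnormal one, and censoring if the last reading is abnormal.

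- *Tympanic, slow fall* (38.4, 37.8, 37.8, 37.7, 37.6, 37.6, 37.5, 37.3, then 37.0 or lower). With ≤ 37.8 the last abnormal value is at 12 h and recovery is at 24 h. With < 37.5 the last abnormal value is at 84 h and recovery is at 96 h.
- *Oral, fast fall* (38.6, 37.6, 37.0, then 36.6 to 36.8), with one reading of 36.0 at Day 14. With 36.1 to 38.0, recovery is at 648 h. With the ceiling alone it is at 24 h.
- *Same oral series, with the 36.0 at Day 28 instead.* With the floor, the subject is censored at 648 h. With the ceiling alone, recovery is at 24 h.

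Two limiting cases follow directly. A subject never above the oral ceiling, whose only abnormal value is 36.0 at Day 28, is censored at the last reading instead of scored 0 h. A subject with every tympanic reading at 37.5 to 37.8 is scored 0 h and is abnormally high at every visit in the safety tables.

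**4. How often low readings could matter**

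Let p be the chance that a reading by one of the three routes with a floor is below 36.1 at a given visit in a subject whose fever has gone. Take visits as independent and count only Days 7, 10, 14 and 28. Then:

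- censored by a low last reading: p
- at least one low reading: 1 − (1 − p)⁴
- delayed but not censored: 1 − (1 − p)⁴ − p

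| p (assumed) | Censored | At least one low | Delayed only |
|---|---|---|---|
| 1% | 1% | 3.9% | 2.9% |
| 5% | 5% | 18.5% | 13.5% |
| 10% | 10% | 34.4% | 24.4% |

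**5. Illustrative simulation**

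This used 20,000 subjects per setting, all readings oral, a starting temperature uniform on 37.8 to 39.5, a half-life of decline with median 24 h, a settled mean of 36.5, 36.7 or 36.9, and an SD of 0.3 or 0.4. All of these are assumptions. The share censored was 0.2% to 13% with the SAP limits, against 0 to 0.2% with the 38.0 ceiling alone. The median recovery time with the floor was 24 h or 48 h later in three of the six settings and the same in the other three.

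**The case against.** The strongest reply is that the limits serve different purposes. A safety flag may reasonably be stricter than an efficacy definition, and a two-sided range suits an endpoint worded as return to the pre-RSV level. The endpoint is also one of many clinical-course measures, and its Kaplan-Meier analysis is described as exploratory.

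Much of this stands for Attachment 1. It is a toxicity table, which the protocol applies to laboratory abnormalities, skin changes and hematology exclusions. For vital signs, protocol 11.10 points to Attachment 6, which has no temperature limit. The oral overlap is thus something to check, not a contradiction. The argument is weaker for the tympanic limit: one SAP defines normal twice for one route and gives no reason. It does not rescue the floor either. If low values were meant to count as not recovered, rectal and tympanic readings would need a floor too.

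Several stronger readings are tempting but are not supported:

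- *The endpoint is wrong in both directions, and febrile subjects are scored as recovered.* This needs a correct limit, and the documents do not say which one is right.
- *The rectal ceiling is the wrong way round.* That depends on how readings at different sites relate, which no section addresses. Only the unexplained 0.8 °C gap is on the page.
- *A large share of recovered subjects will be censored.* Assuming axillary means of 36.3 to 36.6 and SDs of 0.3 to 0.4, normal tails put 5% to 31% of readings below 36.1, but neither those values nor the share of axillary readings is in the documents.
- *Earlier low readings add to the censoring.* They do not. Only the last assessment censors; earlier ones delay the event.
- *Route and chance outweigh resolution of fever.* Showing this would need the route mix and the share of febrile subjects.

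**Conclusion.** The concern holds in a limited form. From the text alone, tympanic readings of 37.5 to 37.8 are classified in opposite ways by SAP Table 1 and SAP 4.3.3. Also from the text alone, a reading below 36.1 by the axillary, forehead or oral route cancels recovery or, as the last reading, censors the subject. Time to normal temperature can thus be shifted later by low readings, and earlier relative to the SAP's own safety limit for tympanic readings.

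The size of either shift cannot be fixed. It depends on the route mix and on temperature distributions that the documents do not give, and every figure above for a share of subjects or a shift in time rests on assumed readings. The net direction is not established. The effect is confined to this secondary endpoint: the primary viral load AUC does not use temperature, and time to clinical stability is built from SpO2, respiratory rate, heart rate and feeding. It should be corrected, but it does not threaten the main conclusion of the trial.

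**What to change.** Before unblinding, amend SAP Table 1 in two ways:

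1. Define return to normal temperature by the upper limit only. Either delete the 36.1 floors or state that a reading below them neither cancels recovery nor censors the subject.
2. Use one tympanic limit in Table 1 and in 4.3.3. The documents do not settle which, so the sponsor should choose it and give the reason.

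In the same edit, the sponsor should check the oral ceiling of 38.0 against the Grade 1 fever band in Attachment 1, and confirm or correct the rectal ceiling of 37.2.

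The cost is a change to one table, the matching line in 4.3.3 and the derivation program. No new data are needed, since the method of each reading is already to be recorded. Choosing limits after unblinding would leave the choice open to the charge that it was driven by the data.
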